### **Randomization and blinding**

Electronic randomization will be performed by a statistician using a computer-generated randomized sequence with a variable block size unknown to the investigators, and then implemented in a RedCAP™ application. It will be sealed in an opaque envelope and handed to the dedicated research staff not involved in patient care and responsible to prepare the blinded syringe. The envelope will be opened at the patient's entry into the operating ward, after confirming that the surgery will be performed. Once the group is assigned to the patient, the research staff will prepare a syringe containing the randomized solution, either esmolol or saline. Each 10ml ampoule contains 100mg of esmolol. Syringe preparation will depend on the patient's adjusted body weight (ABW) and the expected duration of surgery (DOS) in hour as indicated on the surgical booking request. The number of ampoules required (NA) will be calculated according to the following formula (rounded up to nearest whole number):

$$NA = \frac{ABW \times (0.5 + (1.2 \times DOS))}{100}$$

If a syringe recharge is needed during the surgery, a new blinded syringe containing the same substance as the previous one, will be prepared by the dedicated research staff and brought into the operating room.

The patient, the anesthesiologist, the surgeon, the PACU staff and the research team acting as outcome assessors, will all be blinded to the randomization.

### **Monitoring**

Both groups will undergo routine monitoring according to the CSA guidelines, which will encompass non-invasive blood pressure, pulse-oximetry, EKG and a temperature probe. Invasive arterial pressure monitoring will be at the discretion of the anesthesiologist in charge of the patient. The monitoring will be conducted using the Dräger Infinity C700 (Dräger Medical, Lübeck, Germany) monitor. Additionally, all patients will have a unilateral BISTM EEG sensor (Medtronic, Canada) placed on their forehead to monitor the depth of anesthesia. A Train-of-four scan (TOF scan™; Draeger Medical Canada inc., Mississauga, Ontario, Canada) for monitoring neuromuscular function will also be used. It should be noted that this monitoring is not specific to research and is provided to all patients undergoing general anesthesia at our center.

Throughout the entire anesthesia duration, the NOL index finger probe (PMD-200™ device, Medasense Biometrics Ltd, Ramat Gan, Israel) will be applied for monitoring intraoperative nociception.

All intraoperative data and events will be recorded on the research computer, as further described in the dedicated section of the protocol.

### **Anesthesia Protocol**

**Anesthesia induction:** All patients will receive 1g PO acetaminophen with 10mL of water prior to entering the operating room. Standardized general anesthesia (GA) protocol will be administered in both groups following these procedures: induction with intravenous (IV) slow

boluses of lidocaine to numb the vein, propofol 1.5 to 2 mg.kg (ABW), remifentanil with target controlled infusion (TCI) pump and Minto model to reach an effect-site concentration of 3ng.ml, rocuronium 0.8 mg.kg total body weight (TBW), and dexamethasone 4 mg. Videolaryngoscopy (McGrath) and tracheal intubation will be done when TOF < 2/4 and remifentanil TCI plasmatic concentration (Cp) and effect-site concentration (Ce) will reach their target. Once intubated, remifentanil infusion will be reduced to a Ce of 1ng.ml. A no-touch period of 3 minutes will be observed. Patient's installation will then resume. This induction is part of a standard anesthesia and does not involve any research protocol. It is standardized to homogenize our population.

**Intervention:** Patients will be randomized (1:1) in the intervention group and standard care (SOC) group. In the intervention group, intravenous esmolol will be given as a bolus (0.5mg.kg) over 5 minutes, and will be started simultaneously to the remifentanil initiation.

Once the bolus of esmolol is over, a perfusion of 20 mcg.kg.min will be programmed and maintained until the end of the surgery and completion of skin sutures. In the SOC group saline will be used in place of esmolol. According to the latest meta analysis evaluating esmolol in an opioid-sparing strategy (Gelineau et al., 2018), in all opioids-controlled trials, it was given as a bolus followed by an infusion for the duration of surgery. Initial boluses ranged from 0.5 to 2 mg.kg. The infusion rate varied from 5 mcg.kg.min to 300 mcg.kg.min (mostly 5 to 50 mcg.kg.min). The dosages proposed in this protocol are based on these studies and meta-analyses that have used esmolol for morphine-sparing purposes, while maintaining minimal hemodynamic impact, hence the use of much lower dosages.

***Anesthesia maintenance during surgery:***

Nociception management: The remifentanil target controlled infusion will be set at 3 ng.ml prior to the surgical incision, and will be modified according to the NOL index, as described in Figure 1. If the NOL index is > 25 for more than 1 min, we will increase remifentanil TCI by 0.5 ng.ml. This rate will be decreased by steps of 0.25 ng.ml if the NOL index is < 10 for more than 3 min. The minimal remifentanil TCI concentration allowed in the protocol will be 1 ng ml, to ensure a minimal antinociception drug administration in case of inaccuracy of NOL

Index in either group. Furthermore, in the event of a TAM > 120% of its basal level, and despite a NOL Index between 10 and 25, remifentanil will be increased.

Only the **intervention** and **anesthesia maintenance** sections above differ from the usual management of patients under general anesthesia.

In both groups, IV hydromorphone 0.006 mg.kg and ondansetron 4 mg will be administered once pneumoperitoneum is deflated and skin suture is started. Local anesthetic infiltration of the wounds will be performed by the surgical team using a maximum of 30 ml de bupivacaine 0.5%. Remifentanil infusion will be stopped and removed at the start of wound dressing.

Hemodynamic management: Baseline mean arterial blood pressure (MAP) will be defined as the average of three consecutive values taken 1 min apart and determined before the induction of general anesthesia. Intravenous (IV) infusion of norepinephrine will be adjusted to maintain +/- 20% of the baseline values of the pre-anesthesia MAP. Balanced crystalloids will be administered to patients at a rate of 3 ml.kg.h (ABW) throughout the surgery. Intravenous fluid boluses will be administered at the discretion of the anesthesiologist in charge. Perioperative blood management will be done according to guidelines.

Depth of anesthesia management: The maintenance of anesthesia will rely on sevoflurane to reach [0.7–1.2] minimal alveolar concentration (MAC; MAC adjusted to the participant's age) and a BIS index of [40-60]. Sevoflurane will be discontinued when the wound dressing is completed, and participants will be extubated in the operating room and transferred to the post-anesthesia care unit (PACU).

Neuromuscular blockade management: The TOF ratio will be maintained at 0/4 with repeated boluses of 0.1 mg.kg rocuronium. The patient's neuromuscular blockade will be reversed by sugammadex 2 mg.kg to and 4 mg.kg (TBW) according to TOF response, to obtain a minimum ratio of 0.9.

Patient management in PACU: patients will be transferred to the PACU, and as soon as sufficient contact is obtained by the PACU nurses the pain level will be assessed. In the PACU, all the postoperative criteria of the study will be assessed until time of readiness for discharge. According to standard practice, the attendant nurse will administer IV hydromorphone in PACU.

## **D. ENDPOINTS**

### **Primary endpoint**

The primary endpoint is the intraoperative amount of remifentanyl in mcg.kg-1.h-1, administered between the first surgical incision and its discontinuation at wound dressing.

### **Secondary endpoints**

- The NOL Index variation before and after orotracheal intubation and first surgical incision. NOL index will be evaluated 3 minutes after stimulation to record the maximum value and calculate the area under the curve;
- The mean intraoperative BP and HR;
- The intraoperative doses and time weighted average of norepinephrine (mg); ephedrine (mg), glycopyrrolate (mg) and atropine (mg);
- Total time and time weighted average with NOL value above > 25;
- The total time and time weighted average of hypotension (< 20% of the baseline values of the pre-anesthesia mean arterial pressure (MAP) and/or bradycardia (HR < 60 beats/min, or HR < 50 beats/min for a profound bradycardia)) during surgery;
- The time to first analgesic requirement in PACU;
- The amount of morphine equivalent consumption for postoperative pain relief in the post anesthesia care unit (PACU) in both groups.
- The intensity of pain at rest and under stress, using a verbal rating scale (VRS), from arrival to discharge from PACU.

- The Silvermann Integrated Approach (SIA) Score (combining pain score and opioid consumption);
- Postoperative outcomes such as postoperative nausea and vomiting (PONV) and amount of antiemetics used in PACU;
- The time spent in PACU (in minutes);

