## **Hypotheses**

The main hypothesis of this study is to show that patients receiving an intraoperative esmolol infusion during a NOL-guided general anesthesia, will consume a lower amount of intraoperative remifentanyl (mcg.kg-1.h-1) with a reduction of 20 to 30% of intraoperative opioid consumption, without impacting hemodynamic parameters. Upon reproducible nociceptive stimulation such as orotracheal intubation and initial surgical incision, we expect a reduction of the deltaNOL with the administration of esmolol, while still capturing the event on the PMD-200. Finally, once the patient reaches the PACU, we expect a longer time to first opioid, a lower pain score on arrival, a lower opioid consumption, a reduced incidence of PONV, and a shorter PACU stay.

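### Remifentanil titration is active inside the 3-minute window used for the NOL response to incision, so the between-arm AUC difference there is biased towards no difference if esmolol works as hypothesised

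*Protocol*

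**What the plan says.** The first item under Secondary endpoints is "The NOL Index variation before and after orotracheal intubation and first surgical incision", with this measurement rule: "NOL index will be evaluated 3 minutes after stimulation to record the maximum value and calculate the area under the curve". Secondary Objectives, item 1, says the same. A maximum and an AUC need an interval, so the rule has to mean the 3 minutes that follow each stimulus.

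The Hypotheses section treats the two events as parallel examples of "reproducible nociceptive stimulation such as orotracheal intubation and initial surgical incision" and expects a smaller NOL change with esmolol, with the event still visible on the monitor.

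The two windows are handled differently:

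- **Intubation** (Anesthesia Protocol, induction): the remifentanil target is lowered by the same fixed amount in both arms, and then "A no-touch period of 3 minutes will be observed".
- **Incision** (Anesthesia maintenance during surgery): both arms are set to the same target "prior to the surgical incision, and will be modified according to the NOL index, as described in Figure 1". The rule is "If the NOL index is > 25 for more than 1 min, we will increase remifentanil TCI by 0.5" ng/ml. There is a second trigger: when mean arterial pressure exceeds 120% of baseline, then "despite a NOL Index between 10 and 25, remifentanil will be increased".

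No pause in titration after incision is stated in the text. Only the notes to Figure 1 can be read.

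**The concern.** The endpoint is meant to compare the NOL response to a standard stimulus between arms that start from the same remifentanil target. That comparison is clean only while the target stays the same in both arms. The trigger needs a little over 1 minute above 25 and the window lasts 3 minutes, so an increase can fall inside the window. Whether it does depends on the patient's own NOL, which is the outcome being measured.

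If esmolol lowers NOL, saline patients meet the trigger more often. The arm with the larger response is then treated more, and its later NOL values fall. The AUC difference ends up comparing esmolol with saline plus, on average, more added opioid. The same applies to a maximum reached late in the window.

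At stake is a false impression that esmolol hardly changes the NOL response to incision. The Background section says it is unclear how acute esmolol affects monitors of this kind, and incision is one of only two standardised stimuli in the trial that bear on this.

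**Working it through.** **The plan's own figure.** The protocol gives no expected value, SD or power for the NOL response. Its only sample-size figure is 32 per group, for remifentanil consumption. It reproduces: n = 2 × (1.96 + 0.8416)² × 3.24² / (7.98 − 5.59)² = 28.9, so 29 per group; 29 × 1.1 = 31.9, so 32 (29 / 0.9 = 32.2 would give 33). This does not bear on the present point.

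**Timing, from the protocol.** Window: 180 s. Earliest NOL-triggered increase caused by the incision response: just over 60 s, if NOL crosses 25 at the moment of incision. The part of the window after that increase is at most about 180 − 60 = 120 s, or two thirds. A later crossing leaves less.

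**Direction.** The Hypotheses section expects a lower response with esmolol. More saline than esmolol patients then spend over 1 minute above 25, so the NOL trigger adds remifentanil mainly in the saline arm and pulls the AUC difference towards zero. The arm balance of the blood-pressure trigger cannot be settled from the text: the Background says esmolol can lower blood pressure, while the Hypotheses expect no haemodynamic impact.

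**Size, fixed-value illustration (all NOL values assumed).** Let NOL be constant at 40 with saline and 30 with esmolol, so both arms trigger. Without titration the AUC difference is (40 − 30) × 3 = 30 NOL-min. Let each increase produce a linear fall of F points from 65 to 125 s, held to 180 s. The AUC removed is F × (0.5 × 60 + 55) / 60 = 1.417 × F NOL-min.

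- Equal falls of 10 points in both arms: 14.2 is removed from each arm, and the loss of difference is 0.
- Proportional falls of 25% (10 points against 7.5): the loss is 1.417 × 2.5 = 3.5 of 30, or 12%.

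**Size, simulation (all inputs assumed).** 8,000 patients per arm. Mean peak NOL 45 with saline and 35 with esmolol, SD 12. Linear rise from 10 to a peak at a mean of 30, 60 or 120 s, then decay with a half-life of 60, 120 or 300 s. Patients above 25 for more than 60 s receive one step. A weak, slow step removes 20% of the excess over 10, ramping over 120 s; a strong, fast one removes 50% over 60 s. The blood-pressure trigger was not modelled. Selected results for the between-arm AUC difference (NOL-min), without and with in-window titration:

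| Peak / half-life | Weak, slow step | Strong, fast step |
|---|---|---|
| 60 s / 60 s | 15.4 to 14.7 (−5%) | 15.1 to 12.0 (−21%) |
| 60 s / 120 s | 19.4 to 18.3 (−6%) | 19.0 to 14.3 (−25%) |
| 30 s / 300 s | 23.1 to 21.5 (−7%) | 23.6 to 17.2 (−27%) |
| 120 s / 120 s | 18.3 to 17.3 (−6%) | 18.0 to 13.4 (−26%) |

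Over all settings, 77-94% of saline and 46-75% of esmolol patients triggered within the window. The AUC difference shrank by 5-7% with the weak step and 20-27% with the strong one. The difference in maximum changed by about 0% for peaks at 30 or 60 s, and by 5-23% for a peak at 120 s.

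**The case against.** Several objections have force.

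- **Figure 1.** The text refers to it for the titration algorithm, and it is only partly visible. The absence of a hold is established for the text, not for the whole protocol. This stands as a limit.
- **The maximum.** A reader might infer that the whole incision comparison is compromised. It is not: a maximum reached before the first increase cannot be changed by it. The problem lies with the AUC and with late peaks.
- **Whether NOL still registers the event under esmolol.** A reader might infer that this question is undermined too. The documents do not support that. It is a before-and-after question within the esmolol arm, and a patient whose NOL stays above 25 long enough to trigger an increase has already shown the event.
- **A much larger loss.** With saline fixed at 40 and esmolol at 24, one point under the trigger, the untreated difference is 16 × 3 = 48 NOL-min. Saline falls of 5, 10 or 15 points then cost 7.1, 14.2 or 21.3 of it, or about 15%, 30% and 44%. This requires every saline patient and no esmolol patient to trigger, and nothing in the protocol supports those values.
- **Legitimate quantity.** The trial concerns NOL-guided care, so the 3-minute response under titration is worth reporting. This is right, and it argues for keeping the measure. It does not make that measure a comparison at equal remifentanil.
- **An analysis-plan detail.** A supplementary analysis could be left to a statistical analysis plan. But the window and the titration rule are both fixed in the protocol, and they do not fit together there.

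**Conclusion.** The point holds for the incision AUC and for any maximum reached late in the window. As the visible text stands, NOL-driven remifentanil increases can occur within the 3 minutes over which the response is measured. Under the protocol's own hypothesis they occur more often with saline, so the between-arm difference is biased towards no difference.

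The direction rests on two conditions: that esmolol lowers NOL as expected, and that Figure 1 contains no hold. The size is not derivable from the protocol. It depends on when NOL peaks, how long it stays raised and how fast one step acts. The assumed scenarios give near zero if both arms trigger and fall equally, and roughly 5-27% in the simulation.

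An early maximum and the intubation response are unaffected. So is the primary endpoint, which is the titrated remifentanil amount itself. The bias would not create a false finding of benefit. This is a weakness in one secondary endpoint that is worth correcting because the correction is cheap.

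**What to change.** Keep the 3-minute maximum and AUC for both stimuli, so that incision and intubation remain comparable. In Secondary Objectives (item 1) and Secondary endpoints, add for incision:

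1. A prespecified analysis of maximum NOL and time-normalised AUC (AUC divided by observed time) over the first 60 s after incision, or up to the first remifentanil target change for any reason if that comes earlier. The early cut-off covers patients already above 25 before incision and increases triggered by blood pressure; dividing by observed time handles the unequal lengths.
2. A statement that any conclusion about the response at equal remifentanil rests on this analysis, with the 3-minute result read as the response under titration.
3. The share of patients in each arm whose remifentanil target changed within 3 minutes of incision.

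The sponsor should also reconcile the measurement window with the titration rule and state whether Figure 1 contains a hold after incision. No change to the titration rule is proposed.

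The cost is endpoint wording and a small amount of analysis. Under Data Collection Procedures, NOL is already captured electronically with synchronised device times and recorded event times; the times of target changes must be available alongside them. The downside is that a 60 s window is noisier and may miss late peaks, which is why it should be added to the 3-minute measure and not replace it.

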### **Secondary Objectives**

Secondary objectives cover a wide range of concepts, including the hemodynamic impact of esmolol, the pain profile, and the incidence of opioid-related side effects. More specifically, we aim to :

1. compare NOL Index variation before and after orotracheal intubation and first surgical incision. NOL index will be evaluated 3 minutes after stimulations to record the maximum value and calculate the area under the curve ;
2. compare the mean intraoperative BP and HR;
3. compare the intraoperative requirements and time weighted average of norepinephrine, ephedrine, glycopyrrolate and atropine;
4. compare the total time and time weighted average with NOL value above > 25.
5. To compare the total time and time weighted average of hypotension and/or bradycardia during surgery;
6. compare the time to first analgesic requirement in PACU;
7. compare postoperative morphine equivalent consumption in the post anesthesia care unit (PACU);
8. compare the intensity of pain at rest and under stress, using a verbal rating scale (VRS), from arrival to discharge from PACU;
9. To compare Silvermann Integrated Approach (SIA) Score (combining pain score and opioid consumption);
10. assess postoperative outcomes such as postoperative nausea and vomiting (PONV) and amount of antiemetics used in PACU;
11. compare the time spent in PACU.

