## **E. STATISTICAL PLAN**

### **Sample Size Determination and Power**

Based on a recent unpublished trial (MERK study) recently held at our center focusing on colorectal surgeries, we assumed a mean intraoperative remifentanil consumption of 5.59 mcg.kg-1.h-1 and 7.98, respectively in the intervention and control group, with a combined standard deviation of  $\pm 3.24$ . This data is aligned with recently published international data (Sabourdin et al., 2022). With an alpha risk of 5%, a power of 80.0%, a two-tailed test, and an estimated dropout ratio of 10.0%, it was calculated that 32 patients would be required in each group, to detect a 30% reduction in intraoperative remifentanil administration.

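### The hypotension cut-off in a secondary endpoint is written as one fifth of baseline MAP, whereas the protocol's own ±20% band has its lower edge at four fifths

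*Protocol*

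**What the plan says.** The protocol, section D (Secondary endpoints), lists total time and time-weighted average of hypotension and/or bradycardia during surgery. The hypotension part reads "hypotension (< 20% of the baseline values of the pre-anesthesia mean arterial pressure (MAP". Bradycardia has absolute limits: heart rate below 60 beats/min, or below 50 if profound.

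Three other places bear on the reading:

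- Section C, Hemodynamic management: "Intravenous (IV) infusion of norepinephrine will be adjusted to maintain +/- 20% of the baseline values of the pre-anesthesia MAP". Baseline is defined in the same paragraph: "Baseline mean arterial blood pressure (MAP) will be defined as the average of three consecutive values taken 1 min apart", before induction.
- Section C, Nociception management: one remifentanil trigger is worded "in the event of a TAM > 120% of its basal level". TAM is read here as MAP.
- Section B, Secondary Objectives, item 5: "To compare the total time and time weighted average of hypotension and/or bradycardia during surgery". It gives no cut-off.

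The main hypothesis (section B) expects the opioid reduction "without impacting hemodynamic parameters".

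**The concern.** A cut-off expressed as a percentage of baseline is a multiple of baseline, so the endpoint as written counts only MAP under one fifth of the pre-anaesthesia value. Where section C states a percentage of the basal level, it counts from zero: 120% means 1.20 × baseline. In that notation the lower edge of the ±20% band is 80%, and 20% is a different quantity.

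Hypotension is the first adverse reaction listed for esmolol in section F, and this component is the protocol's direct measure of time spent in hypotension. Blood pressure is extracted electronically and analysed in statistical software, so someone must turn the phrase into a numeric rule. A literal rule would give near-zero time in both arms, which could be taken as reassurance. If an analyst notices and substitutes another rule, the threshold has been chosen during analysis and not in advance.

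**Working it through.** **Inputs from the protocol**

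- Endpoint cut-off: below 20% of baseline MAP (section D).
- Management band: baseline ±20% (section C).
- Baseline: mean of three readings one minute apart, before induction (section C).
- Expected duration of surgery: 60 to 180 minutes (section C, Patient population).

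**The plan's own computed figure.** The only one is the sample size of 32 per group, and it does not use the hypotension threshold. The inputs are means of 5.59 and 7.98, SD 3.24, two-sided alpha 5%, power 80% and dropout 10%. The difference is 7.98 − 5.59 = 2.39. Then n = 2 × (1.960 + 0.842)² × 3.24² / 2.39² ≈ 28.8, rounded up to 29 per group. With dropout this becomes 29 × 1.10 = 31.9, or 32; dividing by 0.90 instead gives 32.2, or 33. The stated figure is reproduced and is untouched by this point.

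**The two thresholds.** Let B be baseline MAP.

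- Endpoint as written: MAP < 0.20 × B.
- Lower edge of the band: (1 − 0.20) × B = 0.80 × B.
- Ratio: 0.80 / 0.20 = 4 at every baseline. Gap: 0.60 × B.

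The protocol gives no value for B, so the following baselines are assumed:

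| Assumed baseline (mmHg) | 0.20 × B | 0.80 × B | Gap |
|---|---|---|---|
| 70 | 14 | 56 | 42 |
| 80 | 16 | 64 | 48 |
| 90 | 18 | 72 | 54 |
| 100 | 20 | 80 | 60 |
| 110 | 22 | 88 | 66 |

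**Effect on the endpoint (illustration only).** Assume that intraoperative MAP, as a percentage of baseline, is normal with mean m of 85 to 95 and SD s of 10 to 15, over 120 minutes (the midpoint of 60 and 180). Expected time below a cut-off c is 120 × Φ((c − m)/s).

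- c = 80, m = 95, s = 10: Φ(−1.50) = 0.0668, or 8.0 min.
- c = 80, m = 90, s = 10: Φ(−1.00) = 0.1587, or 19.0 min.
- c = 80, m = 85, s = 15: Φ(−0.33) = 0.3694, or 44.3 min.
- c = 20, m = 85, s = 15 (the largest value in the range): Φ(−4.33) = 7.3 × 10⁻⁶, or 0.0009 min.

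Over these assumptions, time below 80% of baseline is 8 to 44 minutes, and time below 20% is under 0.001 minute.

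**The case against.** The best defence is that the meaning is obvious. Section C uses almost the same phrase, where it can only mean a deviation of 20% from baseline, and an anaesthesia team would read the endpoint as more than 20% below. An outcome of zero in every patient would expose a literal coding at once, and because the pressures are stored electronically the variable could be recomputed. This stands as far as it goes. The intent is probably clear, the harm is avoidable, and the point is a drafting error, not a deliberate choice of threshold. It does not make the written cut-off right, and an operative endpoint definition should not need repair by inference.

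A second objection is that the ±20% band is a norepinephrine titration target and not a definition of hypotension, so an outcome cut-off may legitimately differ from it. That is true, and the mismatch alone would prove little. But one fifth of baseline is not usable as a hypotension threshold on its own terms, whatever the titration target is.

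Third, the time illustration rests on assumed distributions and ignores norepinephrine titration, which would tend to shorten time below 80%. That also stands: the 8 to 44 minutes is no forecast. The factor of 4 between the thresholds needs none of those assumptions.

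Finally, the body of Figure 1 could not be read for this review, and whether it states a pressure limit is unknown. Its surviving footnotes do not define hypotension.

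**Conclusion.** The hypotension threshold is wrong as written. It is one quarter of the value implied by the protocol's ±20% band on the same baseline, and no readable text corrects it. Coded literally, the component would be practically empty in both arms; that rests only on intraoperative MAP almost never falling below one fifth of its pre-anaesthesia value.

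The reach is limited to one component of one secondary endpoint. Bradycardia, mean blood pressure and heart rate, and the doses of norepinephrine, ephedrine, glycopyrrolate and atropine would still carry haemodynamic information. The primary endpoint, alpha, power and the 32 per group do not change. It should be corrected, but it does not threaten the trial's main conclusion.

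**What to change.** Reconcile section D (Secondary endpoints) with section C (Hemodynamic management) before any data are coded. Once the sponsor confirms the evident intent, define the outcome as a fall of more than 20% from the pre-anaesthesia baseline MAP, that is, MAP < 80% of baseline, and point to the baseline definition already in section C. Put the same cut-off, or a reference to it, in item 5 of the Secondary Objectives. Close the bracket after the hypotension criterion so that the heart-rate limits no longer sit inside it.

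This changes outcome measurement only and leaves the norepinephrine and remifentanil rules as they stand. The cost is one phrase and one bracket: no new data, and no change to conduct or sample size.
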